6.2.1.2 Duration of Treatment and Criteria for Retreatment

For patients receiving durvalumab + tremelimumab + olaparib, retreatment is allowed (once only) for patients meeting the retreatment criteria below. The same treatment guidelines followed during the initial 12-month treatment period will be followed during the retreatment period, including the same dose and frequency of treatments and the same schedule of assessments. Similar to the initial treatment, in the event of disease progression while the patient is receiving durvalumab and olaparib alone (i.e. after completion of the first 4 doses of tremelimumab), the patient may be given an additional 4 doses of tremelimumab per the investigator's discretion, in combination with the ongoing durvalumab and olaparib.

Patients receiving the combination of durvalumab, tremelimumab, and olaparib may undergo retreatment in the clinical scenarios described below:

- Patients who achieve and maintain disease control (i.e., irCR, irPR, or irSD) through to the end of the 12-month treatment period may restart treatment with the combination upon evidence of PD according to irRECIST during follow-up.

- Before restarting their assigned treatment, the Investigator should ensure that the patient:
 - Does not have any significant, unacceptable, or irreversible toxicities that indicate continuing treatment will not further benefit the patient.
 - Still fulfills the eligibility criteria for this study, including re-consenting to restart durvalumab, tremelimumab, and olaparib.
 - Has not received an intervening systemic anticancer therapy after their assigned treatment discontinuation.
 - Has had a baseline tumor assessment within 28 days of restarting their assigned treatment; all further scans should occur with the same frequency as during the initial 12 months of treatment (relative to the date of randomization) until study treatment is stopped (maximum of 12 months of further treatment).

During the retreatment period, patients receiving durvalumab + tremelimumab + olaparib may resume durvalumab dosing at 1500 mg Q4W with 75 mg of tremelimumab Q4W for 4 doses each. Patients will then continue with durvalumab monotherapy at 1500 mg Q4W, beginning at Week 16, 4 weeks after the last dose of combination therapy (a total of 9 additional doses). Olaparib will be administered throughout this retreatment period at 300 mg BID (or the MTD in case of dose de-escalation) for up to 1 year.

Treatment through progression is at the Investigator's discretion, and the Investigator should ensure that patients do not have any significant, unacceptable, or irreversible toxicities that indicate that continuing treatment will not further benefit the patient. A patient with a confirmed progression receiving durvalumab + tremelimumab + olaparib cannot continue therapy or obtain retreatment if dosing is ongoing in the combination portion of therapy (Q4W dosing) and progression occurs in a target lesion that has previously shown a confirmed response.

Patients who AstraZeneca and/or the Investigator determine may not continue treatment will enter follow-up. There will be no replacement of patient during retreatment.

6.2.2 Olaparib

Subjects will be administered olaparib in line with normal clinical practice, at 300 mg BID, in combination with fixed doses of durvalumab and tremelimumab. It is expected that subjects will receive this combination therapy for up to 1 year or until disease progression, whichever occurs sooner. After completion of the Phase I portion of the study, the safe dose of olaparib to be used in the Phase II study for this combination therapy was determined to be 250 mg BID.

6.2.2.1 Dose administration

Patients will take 2 tablets of 150 mg each (total 300 mg), orally, twice daily. In case of the reduced 200 mg dose group, patients will take 2 tablets of 100 mg and for the 250 mg dose group, one 150 mg and one 100 mg tablet. The olaparib tablets should be swallowed whole and not chewed, crushed, dissolved or divided. Durvalumab + tremelimumab should be given at least 1 hour after the patient has taken their olaparib morning dose.

6.2.2.2 Monitoring of dose administration

Patients will be monitored for the first dose, similar to as described for durvalumab and tremelimumab (refer to Section 6.2.1.1) and subsequent doses will be taken by the patient at home.

Reported adverse events (AEs) and potential risks are described in Section 1.3.2. Appropriate dose modifications are described in Section 6.5.

6.3 Cohort Management: Dose Escalation Decision Rules

Refer to **Section 4.1**.

Fixed doses of durvalumab, tremelimumab, and olaparib will be used in the first 6 patients in a Phase I safety run part of this study (Safety lead-in Cohort) followed by a Phase II part of the study (expansion cohort), enrolling 27 additional subjects (18 platinum-resistant patients and 9 platinum-sensitive patients). In case of >1 DLT out of the 6 patients, tremelimumab will be eliminated from this combination study (The DLT must be related to tremelimumab). The dose of tremelimumab utilized here is the lowest effective dose and therefore de-escalation not recommended. If the DLT is olaparib related, de-escalation plan is to decrease to 250 mg and then to 200 mg as shown in **Table 1**, following the 3+3 rule.

6.4 Definition of Dose-Limiting Toxicity

Dose-limiting toxicities (DLTs) will be evaluated during the Phase I portion of the trial. The period for evaluating DLTs will be from the time of first administration of durvalumab, tremelimumab, and olaparib until two cycles of durvalumab (8 weeks). Subjects who do not remain on the study up to this time for reasons other than DLT will be replaced with another subject at the same dose level. Grading of DLTs will follow the guidelines provided in the Common Terminology Criteria for Adverse Events (CTCAE) version 4.03.

A DLT will be defined as any Grade 3 or higher toxicity that occurs during the DLT evaluation period. Toxicity that is clearly and directly related to the primary disease or to another etiology is excluded from this definition. The following will be DLTs:

- Any Grade 4 irAE
- Any \geq Grade 3 colitis
- Any Grade 3 or 4 noninfectious pneumonitis irrespective of duration
- Any Grade 2 pneumonitis that does not resolve to \leq Grade 1 within 3 days of the initiation of maximal supportive care
- Any Grade 3 irAE, excluding colitis or pneumonitis, that does not downgrade to Grade 2 within 3 days after onset of the event despite optimal medical management including systemic corticosteroids or does not downgrade to \leq Grade 1 or baseline within 14 days
- Liver transaminase elevation $> 5 \times$ ULN or total bilirubin $> 5 \times$ ULN
- Bone marrow findings consistent with myelodysplastic syndrome/acute myeloid leukemia
- Any \geq Grade 3 non-irAE, except for the exclusions listed below

The definition excludes the following conditions:

- Grade 3 fatigue lasting \leq 7 days
- Grade 3 endocrine disorder (thyroid, pituitary, and/or adrenal insufficiency) that is managed with or without systemic corticosteroid therapy and/or hormone replacement therapy and the subject is asymptomatic
- Grade 3 inflammatory reaction attributed to a local antitumor response (e.g., inflammatory reaction at sites of metastatic disease, lymph nodes, etc)
- Concurrent vitiligo or alopecia of any AE grade
- Grade 3 infusion-related reaction (first occurrence and in the absence of steroid prophylaxis) that resolves within 6 hours with appropriate clinical management
- Grade 3 or 4 neutropenia that is not associated with fever or systemic infection that improves by at least 1 grade within 3 days. Grade 3 or Grade 4 febrile neutropenia will be a DLT regardless of duration or reversibility
- Grade 3 or 4 lymphopenia
- Grade 3 thrombocytopenia that is not associated with clinically significant bleeding that requires medical intervention, and improves by at least 1 grade within 3 days
- Isolated Grade 3 electrolyte abnormalities that are not associated with clinical signs or symptoms and are reversed with appropriate maximal medical intervention within 3 days

Immune-related AEs are defined as AEs of an immune nature (i.e., inflammatory) in the absence of a clear alternative etiology. In the absence of a clinically significant abnormality, repeat laboratory testing will be conducted to confirm significant laboratory findings prior to designation as a DLT.

6.5 Dose Modifications and Toxicity Management

For adverse events (AEs) that are considered at least partly due to administration of durvalumab or tremelimumab or olaparib, the following dose adjustment guidance may be applied:

- Treat each of the toxicities with maximum supportive care (including holding the agent suspected of causing the toxicity where required).
- If the symptoms promptly resolve with supportive care, consideration should be given to continuing the same dose of durvalumab or tremelimumab or olaparib along with appropriate continuing supportive care. If ≥ 2 DLTs due to tremelimumab, tremelimumab will be eliminated for the Phase II expansion cohort. There will be no dose adjustment.

In addition, there are certain circumstances in which durvalumab or tremelimumab should be permanently discontinued.

Management of toxicity of durvalumab and tremelimumab

Based on the mechanism of action of durvalumab or tremelimumab leading to T-cell activation and proliferation, there is the possibility of observing immune related Adverse Events (irAEs) during the conduct of this study. Potential irAEs include immune-mediated enterocolitis, dermatitis, hepatitis, and endocrinopathies. Subjects should be closely monitored for signs and symptoms of irAEs. In the absence of an alternate etiology (e.g., infection or PD) signs or symptoms of enterocolitis, dermatitis, hepatitis, and endocrinopathy should be considered to be immune-related.

Toxicity management guidelines for immune-mediated reactions, for infusion-related reactions, and for non-immune-mediated reactions are detailed in Appendix G.

In addition, management guidelines for adverse events of special interest (AESIs) are detailed in Section 10.2. All toxicities will be graded according to NCI CTCAE v4.03.

Management of toxicity of olaparib

Any toxicity observed during the course of the study could be managed by interruption and/ or dose reduction of the dose if deemed appropriate by the Investigator. Repeat dose interruptions are allowed as required, for a maximum of 14 days on each occasion. If the interruption is any longer than this the AstraZeneca study team must be informed. Olaparib must be interrupted until the patient recovers completely or the toxicity reverts to the National Cancer Institute (NCI) Common Terminology Criteria for Adverse Events (current version) grade 1 or less.

Where toxicity reoccurs following re-challenge with olaparib, and where further dose interruptions are considered inadequate for management of toxicity, then the patient should be considered for dose reduction or must permanently discontinue treatment with olaparib. Dose de-escalation will be to 250 mg BID and then to 200 mg BID if needed.

Treatment must be interrupted if any NCI-CTCAE grade 3 or 4 adverse event occurs which the Investigator considers to be at least possibly related to administration of olaparib.

Management of anemia

Adverse events of anemia CTCAE grade 1 or 2 (Hemoglobin (Hb) > 8 g/dL) should be investigated and managed as deemed appropriate by the investigator with or without interruption of study drug or change in dose, taking into account previous history of anemia. Common treatable causes of anemia (e.g., iron, vitamin B12 or folate deficiencies and hypothyroidism) should be excluded. In some cases, management of anemia may require blood transfusions. However, if a patient develops anemia CTCAE grade 3 (Hb < 8 g/dL) or worse, study treatment should be interrupted for up to maximum of 4 weeks to allow for bone marrow recovery and the patient should be managed appropriately. Study treatment can be restarted at the same dose if Hb has recovered to > 10 g/dL. Any subsequently required anemia related interruptions, considered likely to be dose related, or coexistent with newly developed neutropenia, and or thrombocytopenia, will require study treatment dose reductions by 250 mg bd as a first step and to 200 mg bd as a second step.

If a patient has been treated for anemia with multiple blood transfusions without study treatment interruptions and becomes blood transfusion dependent as judged by investigator, study treatment should be permanently discontinued.

Management of neutropenia and leukopenia

Adverse event of neutropenia and leukopenia should be managed as deemed appropriate by the investigator with close follow up and interruption of study drug if CTC grade 3 or worse neutropenia occurs. Primary prophylaxis with Granulocyte colony-stimulating factor (G-CSF) is not recommended, however, if a patient develops febrile neutropenia, study treatment should be stopped and appropriate management including G-CSF should be given according to local hospital guidelines. Please note that G-CSF should not be used within at least 24 h of the last dose of study treatment.

Study treatment can be restarted at the same dose if an adverse event of neutropenia or leukopenia have been recovered up to CTC AE grade >1 (ANC $> 1.5 \times 10^9/L$). Growth factor support should be stopped at least 24h before restarting study drug (7 days for pegylated G-CSF).

Any subsequent interruptions will require study treatment dose reductions.

Management of thrombocytopenia

An adverse event of thrombocytopenia should be managed as deemed appropriate by the investigator. If a patient develops thrombocytopenia CTCAE grade 3 or worse study treatment should be interrupted for a maximum of 4 weeks. In some cases, management of thrombocytopenia may require platelet transfusions. Platelet transfusions should be done according to local hospital guidelines.

Management of prolonged hematological toxicities while on study treatment

If a patient develops prolonged hematological toxicity such as:

- ≥ 2 week interruption/delay in study treatment due to CTC grade 3 or worse anemia and/or development of blood transfusion dependence
- ≥ 2 week interruption/delay in study treatment due to CTC grade 3 or worse neutropenia (ANC $< 1 \times 10^9/L$)
- ≥ 2 week interruption/delay in study treatment due to CTC grade 3 or worse thrombocytopenia (Platelets $< 50 \times 10^9/L$)

Weekly differential blood counts including reticulocytes (calculate reticulocyte index (RI), RI = reticulocyte count x hematocrit (Hct)/normal Hct; a value of 45 is usually used for normal Hct) and peripheral blood smear should be performed. If any blood parameters remain clinically abnormal after 4 weeks of dose interruption, the patient should be referred to hematologist for further investigations. Bone marrow analysis and/or blood cytogenetic analysis should be considered at this stage according to standard hematological practice.

Myelodysplastic syndrome and/or Acute Myeloid Leukemia (MDS/AML is an important potential risk for olaparib. Development of a confirmed MDS or other clonal blood disorder should be

reported as an SAE and full reports must be provided by the investigator to AstraZeneca Patient Safety. Study treatment should be discontinued if diagnosis of MDS/AML is confirmed.

The dose of olaparib **must not** be adjusted under any other circumstances unless the AstraZeneca Study Physician gives prior agreement.

Management of new or worsening pulmonary symptoms

If new or worsening pulmonary symptoms (e.g. dyspnea) or radiological abnormality occurs, an interruption in olaparib dosing is recommended and a diagnostic workup (including a high-resolution CT scan) should be performed, to exclude pneumonitis. Following investigation, if no evidence of abnormality is observed on CT imaging and symptoms resolve, then olaparib treatment can be restarted, if deemed appropriate by the investigator. If significant pulmonary abnormalities are identified, these need to be discussed with the AstraZeneca Study Physician.

All dose reductions and interruptions (including any missed doses), and the reasons for the reductions/interruptions are to be recorded in the eCRF.

Olaparib should be stopped before surgery and re-started after wound has healed following recovery.

No stoppage of olaparib is required for any biopsy procedures.

Olaparib should be discontinued for a minimum of 7 days before a patient undergoes therapeutic palliative radiation treatment.

Management of nausea and vomiting

Events of nausea and vomiting are known to be associated with olaparib treatment. In study D0810C00019 nausea was reported in 71% of the olaparib treated patients and 36% in the placebo treated patients and vomiting was reported in 34% of the olaparib treated patients and 14% in the placebo treated patients. They are generally mild to moderate (CTCAE grade 1 or 2) severity, intermittent and manageable on continued treatment. The first onset generally occurs in the first month of treatment with the incidence of nausea and vomiting not showing an increase over the treatment cycles.

No routine prophylactic anti-emetic treatment is required at the start of study treatment, however, patients should receive appropriate anti-emetic treatment at the first onset of nausea or vomiting and as required thereafter, in accordance with local treatment practice guidelines.

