4 METHODOLOGY

4.1 Study Design Overview

This is an open-label Phase I/II study for combination of the PARP inhibitor olaparib with anti-PD-L1 antibody durvalumab and anti-CTLA4 antibody tremelimumab, utilizing a 3+3 design. Fixed doses of durvalumab (1500 mg Q4W for up to 1 year) and tremelimumab (75 mg Q4W for 4 cycles) will be utilized with the recommended dose of olaparib for BRCA mutated ovarian cancer (300 mg BID for up to 1 year) in the first 6 patients in a Phase I safety run part of this study (Safety lead-in Cohort) followed by a Phase II part of the study (expansion cohort), enrolling 27 additional subjects. In case of >1 DLT out of the 6 patients, tremelimumab will be eliminated from this combination study as many of the toxicities from durvalumab and tremelimumab overlap but based on published studies, tremelimumab is associated with more frequent and severe side effects. Data suggested that increasing doses of durvalumab may not impact the safety of the combination as much as the tremelimumab dose. The dose of tremelimumab utilized here is the lowest effective dose and therefore de-escalation not recommended. If the DLT is olaparib related, de-escalation plan is to decrease to 250 mg and then to 200 mg as shown in **Table 1**, following the 3+3 rule.

Update: The Phase 1 portion of this study has been completed and reviewed. 6 patients were treated at Dose level -1 (durvalumab 1500 mg + tremelimumab 75 mg + Olaparib 250 mg) with no dose limiting toxicities observed. Based on this, the dose for the Phase II Expansion cohort was determined as **durvalumab 1500 mg IV Q4W up to 1 year + tremelimumab 75 mg IV Q4W 4 cycles + olaparib 250 mg PO BID up to 1 year**.

Table 1 Treatment of Algorithm on True DLT Risk**Phase I:**

Cohort	Dose Level	N	# of DLTs*	Action Based on # of DLTs			Total #	
Phase I Lead-in cohort	durvalumab 1500 mg + tremelimumab 75 mg + olaparib 300 mg	3	0, 1	+ 3	1/6 DLT: Phase II Expansion cohort		6 to 12 depending on DLTs	
			≥ 2	Eliminate tremelimumab: Phase II-T Expansion cohort or If DLT due to olaparib, dose de-escalate olaparib as follows:				
			+3		0/3 DLT: Phase II-O Expansion cohort: durvalumab 1500 mg + tremelimumab 75 mg + olaparib 250 mg			
			+3		1/3 DLT: +3 at same dose			
			durvalumab 1500 mg + tremelimumab 75 mg + olaparib 250 mg		1/6 DLT: Phase II-O Expansion cohort: durvalumab 1500 mg + tremelimumab 75 mg + olaparib 250 mg			

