			+3		≥2/3 or ≥2/6 DLTs: +3 with further de-escalation: durvalumab 1500 mg + tremelimumab 75 mg + olaparib 200 mg			

*DLT – dose limiting toxicity in the first two cycles of treatment.

[figure not shown]
For further description of Table 1, please refer to Section 6.3..

Phase II (Dose determined after completion of the Phase I portion of the study):

Cohort	Dose Level	N	# of DLTs	Action Based on # of DLTs	Total #
Phase II Expansion cohort (2:1 ratio of platinum-resistant to platinum-sensitive)	durvalumab 1500 mg + tremelimumab 75 mg + olaparib 250 mg	27	N/A	N/A	18 platinum-resistant and 9 platinum-sensitive)

The study schema is depicted in Figure 1.

Figure 1 Study Schema

Enrollment into the study will be at a 2:1 ratio of platinum-resistant to platinum-sensitive disease only in the Phase II study. Enrollment into the safety lead-in cohort of the Phase I part will not be constrained to a 2:1 ratio of platinum-resistant to platinum-sensitive disease. Estimated total sample size including the Phase I lead-in and Phase II expansion cohorts, n = 33 to 39. It has been observed that ovarian cancer patients with BRCA1 and BRCA2 mutations tend to be more sensitive to platinum agents and possibly PARP inhibitors than wild-type BRCA ovarian cancers. In an initial proof-of-concept study of 50 BRCA1/BRCA2-mutated patients treated with 200 mg BID olaparib, objective response rates for platinum-sensitive and platinum-resistant cases were 46% and 33%. Therefore, in this combination drug therapy study, the Phase II study is planned to enroll at a 2:1 ratio of platinum-resistant to platinum-sensitive disease.

Durvalumab will be administered every 4 weeks (Q4W) for up to 1 year (13 cycles) and tremelimumab will be administered every 4 weeks (Q4W) for up to 4 doses/cycles. Olaparib will be administered 300 mg BID (or lower in the event of de-escalation) for up to 1 year. Study treatments will be continued for up to 1 year or until disease progression, whichever occurs sooner. Each cycle for durvalumab and tremelimumab is 4 weeks. Olaparib is continuous dosing. For the first 4 cycles (16 weeks), a patient will receive all three drugs and then continue with only

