6 TREATMENT PLAN

6.1 Dosing and Administration

Patients will receive IV infusions of fixed doses of durvalumab (1500 mg Q4W for up to 13 doses/cycles) and tremelimumab (75 mg Q4W for up to 4 doses) in combination with olaparib (300 mg BID or lower in case of de-escalation) orally. Study drugs will be continued for up to 1 year or until disease progression, whichever occurs sooner. After Phase I completion, dose of olaparib for Phase II was determined to be 250 mg BID.

For cohorts receiving all 3 drugs (durvalumab, tremelimumab, and olaparib):

In the event that the patient experiences disease progression during the time that they are receiving durvalumab and olaparib alone (i.e. after first 4 doses of tremelimumab have been completed), an additional 4 doses of tremelimumab may be added to ongoing durvalumab and olaparib at the investigator's discretion.

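### The olaparib reduction steps in Section 6.5 still begin at 250 mg BID, which is now the Phase II starting dose; separately, Section 6.6.3 item 3 states the 10 mg/day steroid limit the wrong way round

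*Combined protocol and SAP*

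**What the plan says.** **Phase II dose.** Section 6.1 states: "After Phase I completion, dose of olaparib for Phase II was determined to be 250 mg BID". Sections 6.2.2 and 8.2 and the update in Section 4.1 agree, and the Phase II part of Table 1 gives the regimen as "durvalumab 1500 mg + tremelimumab 75 mg + olaparib 250 mg" for 27 patients.

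**Olaparib reductions.** Section 6.5 is not limited to Phase I: "Any toxicity observed during the course of the study could be managed by interruption and/ or dose reduction of the dose". When toxicity returns after re-challenge and further interruptions are judged inadequate, the patient "should be considered for dose reduction or must permanently discontinue treatment with olaparib". The sequence follows: "Dose de-escalation will be to 250 mg BID and then to 200 mg BID if needed".

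Under anemia, later interruptions that are thought to be dose related, or that come with new neutropenia or thrombocytopenia, "will require study treatment dose reductions by 250 mg bd as a first step and to 200 mg bd as a second step". Under neutropenia and leukopenia the text is "Any subsequent interruptions will require study treatment dose reductions", with no dose. The thrombocytopenia paragraph gives an interruption limit and no reduced dose. Section 6.5 also bars any other olaparib adjustment unless the supporter's study physician agrees beforehand.

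**Steroids.** Section 6.6.3 item 3 lists systemic corticosteroids at or below 10 mg/day of prednisone equivalent among the excluded medications. Table 3, in the same section, prohibits doses above that level. Item 3 makes exceptions for managing drug-related adverse events, for contrast allergy, for inhaled and intranasal use, and for a temporary course at the investigator's discretion.

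**The concern.** A reduction step has to be lower than the dose the patient is taking. The sections that set the Phase II dose were brought up to date after Phase I, but the toxicity rules were not. The first step in Section 6.5 is therefore the dose that every Phase II patient starts on.

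This matters most in the anemia paragraph, where a reduction is required once the conditions are met. A site that restarted such a patient at 250 mg could point to the text as support, although no reduction would have been made. The neutropenia and leukopenia line depends on the same sequence because it names no dose of its own.

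In the steroid item, a patient correctly enrolled on long-term low-dose prednisone would, on a literal reading, be taking an excluded medication from day 1, while Table 3 would allow it.

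**Working it through.** The plan reports no figure on this point, so there is nothing to reproduce. The check is dose arithmetic plus a comparison of sections.

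**Inputs**
- Starting dose as first planned: 300 mg BID (Sections 4.1, 6.1).
- Phase II starting dose: 250 mg BID (Sections 4.1, 6.1, 6.2.2, 8.2).
- Written steps: 250 mg, then 200 mg BID (Section 6.5).
- Tablet strengths: 100 mg and 150 mg (Section 7.3.1). Section 6.2.2.1 gives tablet instructions for 200 mg: two of 100 mg.
- Planned Phase II enrolment: 18 platinum-resistant + 9 platinum-sensitive = 27 (Table 1).

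**Size of each step**, as (start − step) / start:

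| Start | Written step 1 (250 mg) | Written step 2 (200 mg), from start |
|---|---|---|
| 300 mg | (300 − 250)/300 = 16.7% | (300 − 200)/300 = 33.3% |
| 250 mg | (250 − 250)/250 = 0% | (250 − 200)/250 = 20% |

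A patient starting at 300 mg has two real reductions. A patient starting at 250 mg has one.

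**Where the sequence comes from.** Sections 4.1 and 6.3 use the same two steps for Phase I cohort de-escalation from 300 mg. That the Section 6.5 sequence was written for a 300 mg start is an inference, but 250 mg can be a reduction only from a higher dose.

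**The anemia wording.** Read literally, a reduction by 250 mg gives 250 − 250 = 0 mg, or 300 − 250 = 50 mg. The second is below the smallest tablet. In both cases a second step to 200 mg would be an increase. So 'by' must be a misprint for 'to', and once it is read as 'to', the step from 250 mg is again 0%.

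**Steroid limit, side by side**
- Section 6.6.3 item 3: doses at or below 10 mg/day are excluded.
- Table 3: doses above 10 mg/day are prohibited.
- Appendix G: patients with endocrinopathies needing continued steroid replacement may resume study drug at about that level (at or below 10 mg/day in the Grade 2 text).
- Exclusion criterion 12: up to 10 mg/day is accepted in the 28 days before the first durvalumab dose. This is indirect support, because it governs entry and not on-study use.

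Item 3 is the outlier, and removing one 'not' brings it into line.

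**The case against.** The best reply is that the sequence still works in practice. It names dose levels. A patient at 250 mg who needs a reduction has one lower level listed, 200 mg, and the tablets for it are described. Going from 250 to 250 mg is not a reduction, so few sites would act on that reading. Any other adjustment needs the study physician's agreement, and interruptions beyond 14 days must be reported to the supporter's study team. This stands, and it is why the point is minor. It does not make the wording right: a compulsory safety rule should name the dose for the regimen in use.

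Four stronger readings may tempt a reader, and the documents do not support them.

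- *That Phase II patients have no reduction available.* They have 200 mg.
- *That 33 patients are affected, by adding the 6 treated in Phase I at 250 mg.* Section 4.1 says Phase I is complete, and nothing shows that any of those 6 is still taking olaparib. The supported count is the 27 planned for Phase II, and that is enrolment, not the number who will need a reduction.
- *That recurrence at 200 mg already means permanent discontinuation.* Section 6.5 allows repeated interruptions and turns to reduction or discontinuation only when further interruptions are judged inadequate.
- *That item 3 opens the door to high-dose steroids.* It excludes immunosuppressive medication in general and gives the steroid dose as one example, so higher doses stay excluded. The slip makes the text too strict, not too loose.

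**Conclusion.** Both inconsistencies are in the current text, and both are minor. For the 27 planned Phase II patients the first written olaparib step is a 0% change, and the only real one is 20% (250 to 200 mg BID). The conclusion assumes that 'by' in the anemia rule means 'to', which the arithmetic makes close to certain, and that the neutropenia and leukopenia line relies on the general sequence, since no other is given. The anemia requirement is conditional, so it binds only patients who meet its criteria.

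How many will need a reduction is not estimated. The documents give no reduction rate for this combination; the 4% and 15% in Section 1.3.2.4 come from monotherapy with 400 mg capsules.

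The steroid item contradicts Table 3, with little practical effect given its exceptions. Neither error touches the sample size, error rate, power or primary test.

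**What to change.** 1. In the general and anemia paragraphs of Section 6.5, add: *For patients receiving 250 mg BID, reduce to 200 mg BID.* Refer to this in the neutropenia and leukopenia line.
2. In the anemia paragraph, change 'by' to 'to' before 250 mg, for any patient who started at 300 mg.
3. Leave the existing interruption and discontinuation text unchanged. What follows 200 mg is a clinical decision for the sponsor and should not be introduced as a wording correction.
4. In Section 6.6.3 item 3, delete the 'not' so that doses exceeding 10 mg/day are excluded, as in Table 3.

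The cost is a few words in one amendment and a memo to sites. The doses and tablets are already in the protocol, and there is no statistical cost.
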